- 3). Determine effects of tACS delivered with nested frequencies(multi-frequency signal) vs single frequency tACS, with regard to intrinsic EEG signal, for modulation of SWA coherence and power, as recorded in our overnight EEG sleep data.
- 4). Determine the cumulative effects of tACS delivered in multiple, consecutive nights on underlying EEG signals, sleep architecture, sleep quality and cognitive function among patients with MCI.

5). Determine if tACS is a viable treatment for disturbances of sleep and cognitive performance among patients with MCI.

6). Generate pilot data and manuscripts to support applications for larger randomized placebo-controlled clinical trials.

We hypothesize that through multiple and consecutive sessions, there are cumulative effects of tACS on sleep architecture, with subsequent impacts on cognitive performance, mood and quality of life among normal health adults, older adults, as well as individuals with MCI.

II. BACKGROUND AND SIGNIFICANCE

Transcranial alternating current stimulation (tACS) is a form of transcranial electrical stimulation (tES), similar to transcranial direct current stimulation (tDCS), each of which utilizes scalp electrodes to deliver current at low amperage through brain cortex. In the case of tACS this current is set to alternate in a specific frequency (14). This transcranial current flow has been demonstrated to alter cellular membrane potentials, with subsequent alteration of cortical excitability and synaptic potentiation (10). The use of tES in human trials has increased markedly within the last 15 years, and to date hundreds of trials with thousands of subjects have been reported without any serious side effects (10, 15). The benefits of tES have been demonstrated in treating the cognitive symptoms of many neurological illnesses including Alzheimer's disease, Parkinson's disease, stroke, depression and epilepsy; notably with exceptional tolerability and without any major safety concerns reported (16-22).

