Unique to tACS is the ability to entrain underlying EEG rhythms with subsequent effects on spectral power and coherence of specific EEG frequencies (23). tACS has been demonstrated to modulate multiple domains of cognition and underlying brain networks, in a mechanism that is dependent on both frequency and location of cortical stimulation sites (reviewed in (24)). With respect to sleep modulation, tACS has been demonstrated to enhance slow wave sleep duration and quality in healthy adults, with subsequent improvement of cognitive performance in memory encoding (7, 13, 25). The use of tACS for such studies has until now relied on conventional sleep lab polysomnography for assessment of EEG and delivery of tACS. Recent innovations in EEG and tES technology, however, have now enabled both tES studies (26, 27), and EEG sleep studies (28) to be performed unsupervised in an at-home protocol. Our proposed study will utilize at-home tACS with simultaneous EEG monitoring to demonstrate feasibility in treating and assessing sleep impairment and accompanying cognitive impairment. Data and manuscripts from this work will be used to support applications for funding larger scale studies using remote treatment and assessment, and thus provide a paradigm which is more feasible to translate and implement in clinical settings.

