Total time		Overnight x 1 nights

VISIT TWO

Name of Instrument/tool/procedure	Purpose (i.e. what data is being collected)	Time to complete
Post-procedure questionnaire	Assess for tolerability of device and address any safety concerns	15 minutes
Collection of Equipment	Collect and Inventory Instruments and Hardware	15 minutes
Total time		30 minutes

2. tACS and EEG ARTIFACT REMOVAL OPTIMIZATION-AWAKE

STUDY VISIT

Name of Instrument/tool/procedure	Purpose (i.e. what data is being collected)	Time to complete
Gather informed consent	Gather consent	15 minutes
EEG/tACS recordings	Generate EEG data while tACS is applied during awake state for optimization of artifact removal	60 minutes
Total time		75 minutes

3. tACS NESTING EFFECTS EXPERIMENT IN HEALTHY 18-50

INITIAL VISIT

Name of Instrument/tool/procedure	Purpose (i.e. what data is being collected)	Time to complete
Gather informed consent	Gather consent	15 minutes
EEG/tACS Equipment Trial	Teach subjects proper equipment use/adjust for comfort	45 minutes
Total time		60 minutes

HOME PORTIONS

Name of Instrument/tool/procedure	Purpose (i.e. what data is being collected)	Time to complete
tACS/EEG Stimulation and Recording	Gather EEG data before and after stimulation	overnight
Complete Consensus Sleep Diary	Assess Sleep Quality (after each night of study)	10 minutes
Word Paired-Associate Task	Assess Memory Encoding (before and after sleep)	20 minutes
Finger Tapping Task	Assess Procedural Memory (before and after sleep)	15 minutes
Total time		Overnight x 3 nights (1 week apart for washout)

VISITS TWO, FOUR and SIX

Name of Instrument/tool/procedure	Purpose (i.e. what data is being collected)	Time to complete
Post-procedure questionnaire	Assess for tolerability of device and address any safety concerns	15 minutes
Collection of Sleep Diary and Equipment	Collect and Inventory Instruments and Hardware	15 minutes
Total time		30 minutes

VISITS THREE and FIVE

Name of Instrument/tool/procedure	Purpose (i.e. what data is being collected)	Time to complete
EEG/tACS Equipment Distribution	Ensure subjects remember proper equipment use	20 minutes

Total time		20 minutes
-------------------	--	------------

4. tACS NESTING EFFECTS EXPERIMENT IN OLDER ADULTS

INITIAL VISIT

Name of Instrument/tool/procedure	Purpose (i.e. what data is being collected)	Time to complete
Gather informed consent	Gather consent	15 minutes
EEG/tACS Equipment Trial	Teach subjects proper equipment use/adjust for comfort	45 minutes

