All efforts will be made to protect the confidentiality of research subjects. All electronic data will be collected via REDCap, de-identified by the research team, and stored on their servers. Only study personnel will have access to the data. The dataset will be stored on a computer that is password-protected, virus-protected, and automatically logs the user off after a period of inactivity. The computer is located in a locked office. The computer will be password protected when not in use. All written data will be stored in a locked file cabinet in a private office, the research office of the Department of Neurology. All personnel involved in the study have completed HIPAA training. Any PHI will be stripped from data files (or shredded from written records) within 6 months of the end of the data collection period such that all PHI will be deleted prior to completion of the final data set. Any publication of data will be reported in aggregate.

XV. WITHDRAWAL OF PARTICIPANTS

Subjects will be withdrawn if they experience adverse effects due to tACS application or are unable to tolerate wearing of equipment. Data from subjects that withdraw will be collected and protected, but not utilized in the data analysis. Follow up will only be performed in the case of adverse events to ensure the safety of the patient.

XVI. RISKS TO PARTICIPANTS

tACS

Over 10,000 research subjects had received tES, including tACS, as of 2014, without any serious side effects reported (51). There has been no evidence of seizures, neuronal pathology, edema or neuropsychological damage (15). At-home, unsupervised, application of tES has been demonstrated to be safe and well-tolerated, without any major adverse events or safety concerns (26, 27). During administration of tES, subjects have reported a mild tingling sensation (70.6%), moderate subjective fatigue (35.3%) and a light itching sensation (30.4%). After administration of tES, subjects have reported mild transient headaches (11.8%), nausea (2.9%) and insomnia (0.98%) (52). Our stimulation parameters (maximum current density 0.515 mA/cm²) are far below established safety thresholds of 14.29 mA/cm² (49). All stimulation parameters within this proposal are well below currently accepted safety guidelines for tACS (50).

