With regard to societal benefits, this study will provide data that may benefit patient populations that suffer from primary sleep disorders, as well as poor sleep due to neurologic and psychiatric illness. This study may indicate that home application of tACS during sleep is a practical and affordable treatment for patients. tACS is an inexpensive, noninvasive, and safe intervention, so providing data that supports its efficacy may substantiate its utility in reducing healthcare costs.

XIX. PROVISIONS TO MONITOR THE DATA FOR THE SAFETY OF PARTICIPANTS

Identification and documentation of adverse events will be the responsibility of the PIs and co-investigators, who will also be performing data collection. Reporting of adverse events will be the responsibility of the principal investigator, [name]. A review of summarized safety information will be performed by [name] and will occur after 1 subject has participated in the study as well as midway through data collection. The study will be stopped if any serious adverse event occurs. A statistical interim analysis will not be performed given that this study is minimal risk.

XX. PROVISIONS TO PROTECT THE PRIVACY INTERESTS OF PARTICIPANTS

All efforts will be made to protect the privacy of research subjects. However, since this study does not involve sensitive data, no privacy measures will be taken other than the data management steps outlined in section XIV.

XXI. MEDICAL CARE AND COMPENSATION FOR INJURY

Medical care and compensation for injury are not applicable given that this is a minimal risk study.

XXII. COST TO PARTICIPANTS

There are no costs to subjects.

XXIII. DRUG ADMINISTRATION

Not applicable.

XXIV. INVESTIGATIONAL DEVICES

The StarStim (<http://www.neuroelectrics.com>) stimulator qualifies as an investigational device. It will deliver the tACS to the patient. The device is battery powered and controlled by a microprocessor for

safety monitoring and to ensure precise current delivery. The device consists of a stimulator, a programmer, and EEG recorder and a set of electrodes. The device is programmed with safety features to limit current intensity, voltage, and impedance to assure stimulation is kept well below accepted safety guidelines, and has been designed to allow safe at-home use. There are no anticipated changes to the device during the course of this study. Starstim is considered a non-significant risk device, as defined under 21 C.F.R. § 812.3(m).

XXV. MULTI-SITE STUDIES

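### Section XV excludes withdrawn subjects from the analysis with no safety or tolerability exception, so a withdrawal or intolerance rate on the analysed set is 0% by construction

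*Protocol*

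**What the plan says.** Two neighbouring sentences in Protocol Section XV matter. The first gives the grounds for withdrawal: "Subjects will be withdrawn if they experience adverse effects due to tACS application or are unable to tolerate wearing of equipment". The second gives the consequence: "Data from subjects that withdraw will be collected and protected, but not utilized in the data analysis". A third limits what happens afterwards: "Follow up will only be performed in the case of adverse events to ensure the safety of the patient".

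Elsewhere the protocol sets goals for which such failures are relevant evidence:

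- Specific Aim 5 (Section I): "Determine if tACS is a viable treatment for disturbances of sleep and cognitive performance among patients with MCI".
- Section II says the at-home set-up is meant to "demonstrate feasibility in treating and assessing sleep impairment and accompanying cognitive impairment".
- The visit tables in Section XII schedule a post-procedure questionnaire in the four home branches, with the purpose "Assess for tolerability of device and address any safety concerns". The awake optimization branch has none.

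Safety monitoring is described separately in Section XIX: "Identification and documentation of adverse events will be the responsibility of the PIs and co-investigators". Summarised safety information is reviewed after one subject and again midway through data collection.

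The SAP lists EEG, sleep, HADS, CGIC and cognitive analyses. It names no analysis set and plans no summary of tolerability, withdrawal or feasibility.

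**The concern.** Read together, the two sentences define the analysed set partly by the outcome that a tolerability assessment would measure. Someone who could not wear the cap, or who was withdrawn because of the stimulation, is by rule not in the analysis. A failure rate computed there carries no information about how often failure occurs.

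This matters because unsupervised home use, in people who need a study partner to apply the equipment, is part of what the project hopes to show, and its results are meant to support larger trials. A designer of such a trial would want to know how many people started, how many stopped, and why. Under Section XV as written, the analysed data cannot give that.

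**Working it through.** **No figure to reproduce.** Neither document states a tolerability, withdrawal or feasibility rate, target or threshold. The check is therefore a logical step followed by an illustration from the protocol's own enrolment numbers.

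**Step 1: the logical step.** Let w be the proportion of enrolled subjects withdrawn for adverse effects or intolerance.

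- On all enrolled subjects, the rate is w.
- On the set left after the Section XV exclusion, the count of such subjects is 0, so the rate is 0% for every w.

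This holds for failure that leads to withdrawal. It does not hold for milder complaints, which a completer can still report.

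**Step 2: inputs for the illustration** (Protocol Section IV, MCI branch).

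- Enrolled: 35. Required: 30.
- Allowance: 35 − 30 = 5, or 5/35 = 14.3%, covering screening failure, unusable data and drop-out together.
- The split among these causes is not given. Let k be the number lost to adverse effects or intolerance, with k from 0 to 5. Assume the whole allowance is used, so that 30 are analysed.

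**Step 3: rate on all enrolled, k/35.**

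| k | all enrolled | analysed set |
|---|---|---|
| 0 | 0% | 0/30 |
| 1 | 2.9% | 0/30 |
| 2 | 5.7% | 0/30 |
| 3 | 8.6% | 0/30 |
| 4 | 11.4% | 0/30 |
| 5 | 14.3% | 0/30 |

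**Step 4: exact (Clopper-Pearson) 95% limits.**

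- Analysed set, 0 of 30: upper limit = 1 − 0.025^(1/30) = 0.116, or 11.6%.
- All enrolled, 5 of 35: lower limit = 2.5% point of Beta(5, 31) = 4.8%; upper limit = 97.5% point of Beta(6, 30) = 30.3%.

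At k = 5 the analysed-set interval (0% to 11.6%) excludes the 14.3% actually seen among those enrolled. At k = 4 or fewer it does not (4/35 = 11.4%), although the point estimate is still 0%. At k = 0 the two sets agree and nothing is distorted.

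**Step 5: do other passages restore these subjects?**

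- Section XIX documents adverse events and is not limited to completers. It sets no final summary by condition and no denominator, and does not mention equipment intolerance or nights completed.
- Section XVII adds review of session logs and asking subjects about side effects, as risk management.
- The SAP is silent.

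The raw information will exist, because Section XV itself says withdrawn subjects' data are collected. What is missing is any plan to use it. Section XV read literally keeps it out of the analysis.

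**The case against.** The strongest reply is that the data analysis meant in Section XV is the EEG, sleep and cognitive analysis, since those are the only outcomes listed, and that safety is handled under Section XIX. On that reading no planned tolerability result is biased, because none is planned. This is fair and it narrows the point: the defect is an exclusion rule without an exemption, combined with the absence of a tolerability endpoint or denominator. It does not remove the point, because nothing in either document says that tolerability summaries fall outside Section XV.

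Aim 5 can also be read as an efficacy question. That stands in part. The aim concerns MCI only, and tolerability is at most one component of viability. The feasibility statement is in the Background section and is not a numbered aim.

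A reader might infer more than the documents support:

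- *That every tolerability or viability result must show almost no failures.* Completers' questionnaires and the Section XIX records can still show problems.
- *That the adverse-effect rate itself will be 0%.* This would require every effect, however mild, to force withdrawal. Section XV can be read so. But Section XVI cites tingling in 70.6% of tES subjects, and Section XVII treats the listed effects as mild and to be minimised. The documents leave the threshold unclear.
- *That only treatment and device failures are dropped.* The sentence covers everyone who withdraws, including for unrelated reasons.
- *That the randomised EEG comparison is shown to be biased.* Sham delivers no current, so withdrawals for effects of tACS could fall unevenly between the MCI arms. That is a separate question, which this check does not settle.

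**Conclusion.** The concern holds in a limited form. A withdrawal or intolerance rate on the analysed set is 0% by definition, and tolerability summaries on that set are biased towards fewer problems. No passage restores the withdrawn subjects for the tolerability side of Aim 5 or the home-feasibility objective.

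The size is unknown. In the MCI branch it ranges from no distortion (k = 0) to 14.3% (95% CI 4.8% to 30.3%) shown as 0/30 (upper limit 11.6%) when k = 5. The upper case assumes that the whole enrolment allowance is used and that every loss is due to adverse effects or intolerance; the documents support neither assumption as likely. The conclusion also assumes that Section XV is applied as written to tolerability summaries, which the text permits but does not spell out.

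This should be corrected. It does not show that safety data are discarded or that a stated result is wrong.

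**What to change.** In Section XV and the SAP, state that the exclusion does not apply to safety, tolerability or feasibility summaries. Suggested text:

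> Adverse effects, device intolerance, withdrawal with reason, and nights completed will be summarised by condition for every subject who wore the equipment for at least one night or session, including subjects who withdrew. This set will be used for the tolerability part of the Aim 5 and home-feasibility conclusions.

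Two details need settling with it:

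- Say whether the equipment trial at the initial visit counts as a session. Otherwise a subject who cannot tolerate the cap there drops out of view.
- Record the reason at the time of withdrawal, because later follow-up is limited to adverse events.

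Separately, Section XV and Sections XVI and XVII should be reconciled on whether mild effects lead to withdrawal. That is for the investigators to decide; the summary above works under either answer.

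The cost is wording and one small table from data the protocol already collects. In the awake branch, which has no questionnaire, the summary would rest on adverse event and withdrawal records. Reported tolerability may look less favourable than it would on completers alone.

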Name of Instrument/tool/procedure	Purpose (i.e. what data is being collected)	Time to complete
Post-procedure questionnaire	Assess for tolerability of device and address any safety concerns	15 minutes
HADS	Assess anxiety and depression (to be administered for MCI trial)	5 minutes
CGIC	Assess Global Impression (to be administered for MCI trial)	5 minutes
Collection of Sleep Diary and Equipment	Collect and Inventory Instruments and Hardware	15 minutes
Total time		30-40 minutes

VISITS THREE and FIVE

Name of Instrument/tool/procedure	Purpose (i.e. what data is being collected)	Time to complete
EEG/tACS Equipment Distribution	Ensure subjects remember proper equipment use	20 minutes
Total time		20 minutes

Location

Pre- and post-test sessions will occur in Building 500 of the Anschutz Medical Campus. Testing will occur at the subjects' homes.

tACS Procedure

tACS or sham will be administered using the StarStim stimulator. Anodes of the tACS stimulator will be placed bilaterally at frontal positions on a 10-20 EEG Electrode Placement System and the cathodes will be placed bilaterally on the posterior regions. Oscillating stimulation, ranging between 0 mA to 2.0 mA (maximum current density 0.515 mA/cm²) will be applied through electrodes in trains up to ten minutes, at frequencies between 0 to 500 Hz in the tACS treatment groups while subjects are in stable stage 2 or deeper NREM sleep on EEG recording (total stimulation time not to exceed 60 minutes). This is similar to prior tACS sleep studies which have safely utilized stimulation protocols within this frequency range (7, 46-48). Our maximum current density is within guidelines of established protocols, and is well below safety thresholds of 14.29 mA/cm² from data obtained in animal models (49). All stimulation

parameters are well below currently accepted safety guidelines for tACS (50). Sham condition will be application of electrodes, without activation of current stimulation. The StarStim tACS device is designed to turn on and off automatically, without need for subject control.

XIII. SPECIMEN MANAGEMENT

There will be no specimens taken in this study.

XIV. DATA MANAGEMENT

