Independently-constructed and direct-to-consumer tES devices have been utilized in the home setting, and in scientific study, without any reported significant adverse events and are considered to be safe for use without food and drug administration (FDA) oversight (53, 54). Direct-to-consumer tES devices include the Thynk (<http://www.thynk.com/>; ©THYNK) and Foc.us (<http://www.foc.us/>; ©FOC.US), which are marketed for multiple purposes including mood regulation, athletic performance, and cognitive enhancement. The Foc.us device is further marketed for sleep enhancement, and is available with a sleep kit to apply tACS at home by consumers. Additional consumer applications include the Halo Sport (<http://www.haloneuro.com/>; ©HALO NEUROSCIENCE) tES device, which is available direct-to-consumer without physician or FDA oversight, has been trialed for athletic training by several athletic organizations, including the US Ski and Snowboarding Association (USSA) national Olympic governing body (<http://ussa.org/>) (55).

The Starstim device, as detailed below, is considered a non-significant risk device, as defined under 21 C.F.R. § 812.3(m). Safety features include integrated limited of current intensity, voltage, and impedance to assure stimulation is kept well below accepted safety guidelines. This device has been designed to allow safe at-home use.

EEG

EEG is a passive recording technology and has been utilized with simultaneous tES devices without any reported major side effects or complications (23, 56). Participants will be assessed for discomfort of the EEG cap prior to its use.

XVII. MANAGEMENT OF RISKS

There are no major risks associated with this study. Regarding the mild tACS side effects listed above, we will minimize these by use of a device with automatic limits of current intensity, voltage, and impedance. Additionally, we will review of tACS session logs, verification of tACS delivery by EEG recording, and patient report inquiry for any side effects.

XVIII. POTENTIAL BENEFITS

Subjects are not expected to benefit from this study. However the risks to participants are minimal given the following: 1) tACS is well tolerated and not associated with any serious adverse side effects 2) The data is not sensitive.

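### Section XV assures no side-effect questionnaire, and in the MCI branch no final HADS or CGIC, for subjects who stop without a recognised adverse event

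*Protocol*

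**What the plan says.** Protocol Section XV has three sentences. The first gives the grounds for withdrawal: "Subjects will be withdrawn if they experience adverse effects due to tACS application or are unable to tolerate wearing of equipment". The second deals with the data: "Data from subjects that withdraw will be collected and protected, but not utilized in the data analysis". The third deals with contact afterwards: "Follow up will only be performed in the case of adverse events to ensure the safety of the patient".

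The scheduled instrument for side effects is the post-procedure questionnaire in Section XII, whose stated purpose is "Assess for tolerability of device and address any safety concerns". In the home-sleep branches it is listed at the visit where staff also "Collect and Inventory Instruments and Hardware". In the MCI branch the HADS and CGIC are listed at those visits too (two, four and six), as well as at the initial visit. No branch lists an early-termination visit.

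Section XVII adds, as a risk-management step, "patient report inquiry for any side effects". It gives no timing and does not mention withdrawn subjects. Section XIX makes the investigators responsible for identifying and documenting adverse events.

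Section IV.5 names the HADS and CGIC as secondary outcomes of the MCI trial, and the SAP lists both among its planned secondary analyses. The SAP does not mention withdrawn subjects.

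**The concern.** The word *only* in Section XV makes contact after withdrawal depend on an adverse event, while the instrument designed to find side effects is given at a visit that the withdrawn subject has no stated reason to attend. Section XV also lists intolerance of the equipment separately from adverse effects, so a subject who stops for that reason falls outside the follow-up rule on its plain wording. Stimulation is given overnight at home, and Section XVI itself cites effects reported after stimulation (headache, nausea, insomnia).

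Two things are at stake. First, the side-effect summary, and the safety reviews in Section XIX that depend on it, could be incomplete for some subjects who stopped. Second, the MCI branch is a parallel 1:1 comparison in which sham delivers no current and adverse effects of tACS are a ground for withdrawal, so stopping can depend on arm. If those who stop have no final HADS or CGIC, nobody can later check whether the completers differ from them.

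**Working it through.** The point is procedural, so the texts come first; the arithmetic only gives scale.

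**Step 1: who is left uncovered.**

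- Recognised adverse effect: Section XV follow-up applies. Covered.
- Cross-over subject (healthy 18-50, older adults) who stops between sessions: the equipment has been handed back, and the questionnaire is listed at that same visit. Covered for the sessions completed.
- Awake optimisation: one laboratory visit, no home portion. Not affected.
- Subject who stops during a home night, or during the MCI week, with no recognised adverse event: outside the Section XV rule, with no early-termination visit. **Not assured.**

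The MCI tables do not tie visits two, four and six to particular nights of the seven. A subject who stops may therefore have had an interim HADS and CGIC. It is the final one that is not assured.

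**Step 2: how many could be affected.** The documents give no expected number of withdrawals. The nearest figure is the MCI allowance in Section IV.5: enrol 35 to have 30.

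- 35 − 30 = 5, and 5/35 = 14.3%.

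The same 5 must also cover screening failures and unusable data, so within that allowance 5 is an upper bound on withdrawals. Below, k = 1 to 5 is an assumption.

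**Step 3: side effects.** Inputs are the post-stimulation rates cited in Section XVI: headache 11.8%, nausea 2.9%. Assume that k stimulated subjects are not asked, that these rates apply to them, and that they are independent. The chance that at least one had the effect is 1 − (1 − p)^k.

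| k | headache, p = 0.118 |
|---|---|
| 1 | 1 − 0.882 = 11.8% |
| 2 | 1 − 0.882² = 22.2% |
| 3 | 1 − 0.882³ = 31.4% |
| 5 | 1 − 0.882⁵ = 46.6% |

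For nausea the range is 2.9% (k = 1) to 1 − 0.971⁵ = 13.7% (k = 5). A side-effect percentage with all 35 MCI subjects as denominator could move by at most k/35, which is 2.9 to 14.3 points.

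**Step 4: MCI outcomes, outer case.** Put all 5 losses in one arm of 35/2 = 17.5, and assume those lost differ from completers by 0.5 to 1 SD.

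- Fraction missing in that arm: 5/17.5 = 28.6%.
- Shift in the completer mean: 0.286 × 0.5 = 0.14 SD, up to 0.286 × 1 = 0.29 SD.
- Standard error of the arm difference at 15 per arm: √(1/15 + 1/15) = 0.365 SD.

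Even this case stays below one standard error. If the losses were split evenly with similar differences, the shifts would largely cancel.

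**Step 5: collection against analysis.** The second sentence of Section XV leaves withdrawn subjects' data out of the analysis. While it stands, a final HADS or CGIC from a withdrawn subject would be stored and not used, so better collection alone would change no result.

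**The case against.** A reader might infer that withdrawn subjects are never asked about side effects unless an event is already known, and that their MCI outcomes are never collected. The documents do not support that. Section XVII plans a side-effect inquiry without limiting it to completers, Section XIX puts no such limit on the investigators' duty to identify adverse events, and Section XV says that withdrawn subjects' data are collected, without saying whether that extends past withdrawal. Follow-up could mean continued contact after an exit visit. A subject who brings the equipment back would plausibly be given the forms listed for that visit. The text is silent, and silence is not a prohibition.

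Two further inferences also fail. It is tempting to say that every withdrawn subject still holds the device; cross-over subjects between sessions do not. It is also tempting to say that the rule misses those most likely to have side effects; subjects with a recognised adverse effect are the ones it follows.

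Finally, the MCI outcomes at issue are secondary, and an exit form cannot recover the primary one, EEG power around each stimulation train.

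All of this stands and limits the point. What it does not supply is a procedure for the subject who stops mid-session or mid-week. Staff have a restrictive sentence in Section XV, a general one in Section XVII, and no rule for choosing between them.

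**Conclusion.** The point holds as a gap in assured collection, confined to subjects who stop during a home session or during the MCI week without a recognised adverse event. For them neither the questionnaire nor, in the MCI branch, the final HADS and CGIC is assured, and Sections XV and XVII sit uneasily together.

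The size is modest and rests on assumptions. The 12% to 47% chance of missing at least one headache requires 1 to 5 stimulated subjects who really are not asked, and the cited 11.8% rate to apply to them. The upper end uses the entire MCI allowance. The shift of 0.14 to 0.29 SD in HADS or CGIC combines three unfavourable assumptions and should be read as an outer case, not as evidence that the MCI comparison is biased. The reason to act is that the remedy is cheap and uncollected data cannot be recovered later.

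**What to change.** 1. Keep the adverse-event follow-up sentence in Section XV; it is that section's only provision for following adverse events after withdrawal. Add after it: *Every withdrawn subject who has begun a tACS or sham home session will be offered the post-procedure questionnaire at equipment return, or by contact, whatever the reason for withdrawal. In the MCI branch the HADS and CGIC will be offered as well. Subjects may decline.*
2. Record the reason for withdrawal by condition. In the MCI branch also record the number of nights completed, so that an early HADS or CGIC can be read as such.
3. State in Section XVII that the side-effect inquiry includes withdrawn subjects, so that the two sections agree.
4. Amend the preceding sentence of Section XV so that withdrawn subjects' HADS and CGIC enter the tACS-sham comparison and their side-effect data enter the safety summary. Add a matching line to the SAP. Without this step the added HADS and CGIC would affect no conclusion.

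The withdrawal criteria and the medical handling of adverse events stay as they are.

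The cost is a short amendment and, per withdrawn subject, the times already listed in Section XII: 15 minutes for the questionnaire, or 15 + 5 + 5 = 25 minutes with the HADS and CGIC. No new forms are needed.
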